## I. BACKGROUND AND SIGNIFICANCE

### A. Historical background

An estimated 68-80% of homeless adults are cigarette smokers, in contrast to the 18% prevalence in the U.S. general population. The health impact of this disparity is substantial. Obstructive lung disease is more than twice as prevalent among homeless individuals than in the US general population, contributing to higher rates of death due to COPD and other respiratory causes. Heart disease is a major cause of death among homeless adults, and several studies have shown higher rates of mortality due to circulatory system diseases among homeless persons in comparison to non-homeless counterparts. In a series of epidemiologic studies of 28,033 homeless adults in Boston, we found that one-third of incident cancers in this cohort were smoking-attributable, and the age-adjusted lung cancer incidence and mortality rates were over 2-fold higher than in Massachusetts adults. These findings contributed to 3- to 5-fold higher rates of death due to any tobacco-attributable cause relative to rates in the Massachusetts general population.

Homeless smokers are interested in quitting. In 2002, Butler et al. reported that 56% of homeless smokers were contemplative about quitting and 17% were in preparation to quit; the level of interest in smoking cessation programs was not significantly different from that seen in low-income non-homeless smokers. In the same year, Connor et al. found that 37% of homeless smokers were ready to quit within the next 6 months. In 2004, Arnsten et al. reported that 44% of homeless smokers were somewhat or very interested in smoking cessation counseling, and 19% were either preparing or trying to quit. In a nationwide study of homeless and non-homeless community health center patients in the United States, we found that currently and formerly homeless smokers did not differ from never-homeless smokers in their past-year desire to stop smoking. In a 2014 survey of 306 homeless smokers at Boston Health Care for the Homeless Program (BHCHP), 62% of participants had intentionally quit smoking for at least 24 hours in the past year and 85% planned to quit smoking in the future, including 24% who planned to do so in the next month.

Despite their interest, few homeless smokers are able to quit and self-efficacy for quitting may be low. [name] and Rigotti found a quit ratio (the proportion of ever-smokers who are former smokers) of 9% in a national sample of homeless adults, a figure one-fifth of that observed in the US general population. The pervasiveness and social acceptability of smoking in the setting of homelessness may be one explanation for the low success rate. Homeless smokers are continuously confronted with social cues to smoke. In a survey of homeless smokers in Dallas, participants reported contact with a mean of 43 other smokers each day. Additionally, homeless smokers are a vulnerable subset of homeless individuals; they are more likely to have histories of childhood adversity, physical or sexual assault, and alcohol or drug use problems. In comparison to non-homeless smokers, homeless smokers begin smoking at

[figure not shown]
an earlier age and smoke more heavily, with a tendency toward higher levels of nicotine dependence. Many homeless smokers report difficulty accessing cessation therapies, which may be due in part to the high rates of lacking health insurance and lacking a usual source of care in this population.

[figure not shown]
Few RCTs of smoking cessation interventions have been conducted for homeless smokers. In 2001, an RCT comparing usual care to multicomponent smoking treatment consisting of 2 counseling strategies coupled with nicotine replacement therapy (NRT) in homeless substance-dependent smokers in a residential rehabilitation program resulted in 10-12% abstinence rates at 1 year in the intervention groups compared to 0% in the usual care group. A 2004 pilot RCT comparing 2 motivational interviewing (MI) protocols coupled with NRT for homeless smokers showed modest 7-day abstinence rates at 26 weeks (8.7% and 17.4%). In 2009-10, the largest RCT of homeless smokers to date randomized 430 participants to nicotine patch treatment with or without MI. Point-prevalence abstinence rates at 6 months were similarly low for both arms (9.3% vs. 5.6%,  $p=0.15$ ). The modest results of these high-quality studies suggest that the optimal approach to promoting smoking cessation among homeless people remains uncertain.

### B. Preliminary data

In October 2015-June 2016, we conducted a pilot RCT of financial incentives for smoking abstinence among homeless smokers at BHCHP. Participants were offered 8 weeks of transdermal nicotine patches and 8 15-minute sessions of behavioral counseling, with (N=25) or without (N=25) escalating financial rewards for brief smoking abstinence, defined as an exhaled CO level <8 ppm. After randomization, participants were asked to make 14 assessment visits over 8 weeks: 3 times per week during weeks 1-2, 2 times per week during weeks 3-4, and once per week during weeks 5-8. Control arm participants received a \$10 payment at each visit, regardless of whether they were abstinent. Incentive arm participants received a payment only if they were abstinent. Payments began at \$15 and increased in \$5 increments with each successive abstinent measurement, up to a maximum of \$35. Non-abstinence or non-attendance resulted in no payment and reset subsequent payments to the starting value of \$15. Payments were issued electronically in real-time onto study-supplied debit cards that could be used at any retail outlet. The primary outcome was a repeated measure of CO-defined abstinence (CO <8 ppm) across the 14 assessment visits. Sensitivity analyses incorporated self-reported abstinence duration.

Two-thirds of eligible individuals participated in the RCT, and we reached our target enrollment within 6 months. Participants attended a median of 10 (of 14) assessment visits, with 98% attending  $\geq 1$  visit and 78% attending  $\geq 7$  visits. Across all 14 time points, CO-defined smoking abstinence was substantially higher in the incentives arm than in the control arm (ranges: 32-68% vs. 0-20%; overall OR 7.28, 95% CI 2.89-18.3; Figure 1). At 8 weeks, 48% of incentive arm participants and 8% of control arm participants had an exhaled CO <8 ppm ( $P=0.004$ ; Figure 2). In a sensitivity analysis incorporating self-report of not smoking all or part of a cigarette in  $\geq$

### C. Study rationale

Our pilot RCT results, together with the findings of prior non-randomized and single-group studies, suggest that financial incentives are a promising approach for reducing smoking in this vulnerable population while pointing toward the need for modifications to improve the duration of on-treatment abstinence and an assessment of post-treatment effects. In addition, little is known about mechanisms of action and contextual factors that may influence on-treatment and post-treatment response to financial incentives in the setting of homelessness.

Initially we had planned to implement an augmented version of our pilot trial. Participants were to be offered the opportunity to attend frequent study visits and receive payments for short-term smoking abstinence, confirmed via a reusable CO monitoring device into which participants would deliberately and forcefully exhale in an indoor space. Unique to the current trial, we would have also assessed long-term smoking abstinence using urine anabasine testing at various timepoints. In view of the ongoing COVID-19 pandemic, we revisited the safety of these study procedures and decided that modifications were needed in order to minimize the risk of COVID-19 transmission among participants and staff.

The chief modification was to remove CO breath testing. However, relying solely on urine anabasine testing for abstinence verification was not desirable as this test does not provide results at the point of care. As a result, the trial would lose the opportunity for immediate reinforcement payments, which are critical in contingency management. As an alternative, we now propose using point-of-care salivary cotinine testing to verify smoking abstinence. Cotinine is a major metabolite of nicotine that can be detected in saliva and urine. Saliva testing is less intrusive than urine testing and would lead to a lower transmission risk of COVID-19 compared to CO breath testing. Additionally, saliva cotinine has a half-life of about 16 hours, which is similar to urine anabasine and much longer than that of breath CO. Therefore monitoring visits would not need to occur as frequently, reducing in-person contact for both participants and study staff.

One complication of switching to cotinine testing is that nicotine replacement therapy (e.g. nicotine patches, lozenges, etc.) cannot be used by participants as a smoking cessation aid as this will interfere with cotinine measurement. To align with current standards of care for treating tobacco use, we felt it was important that participants were offered some type of cessation medication during the study. Based on available evidence and updated recommendations from the American Thoracic Society, we concluded that varenicline was the best option. Varenicline

is an FDA-approved prescription smoking cessation medication that acts as a partial agonist/antagonist at nicotinic receptors, easing withdrawal symptoms while also blocking the rewarding effects of nicotine from cigarettes. Varenicline is now strongly recommended as a first-line smoking cessation medication in virtually all patient populations. Research suggests that varenicline is superior in producing short-term and long-term abstinence compared to bupropion while also producing higher continuous abstinence rates than NRT. When paired with counseling, varenicline is the most effective smoking cessation medication available. Varenicline has also been shown to be safe and effective in at-risk populations, including those with comorbid psychiatric conditions, alcohol use disorder and substance use disorders. To date there has been limited research on the use of varenicline in homeless populations. Therefore, the results of the current study may provide further insight on the uptake of and adherence to varenicline in a homeless population.

## II. SPECIFIC AIMS

To address the above gaps in evidence, we will conduct a community-based RCT of financial incentives for smoking abstinence among adult smokers at BHCHP. Recognized as a leader in homeless health care, BHCHP serves 12,000 currently and formerly homeless patients annually throughout greater Boston. We will randomize 180 participants recruited from 3 BHCHP sites: a shelter clinic, a day center clinic, and a medical center clinic. All participants will be offered 12 weeks of varenicline, 5 sessions of tobacco coaching, and 10 cotinine monitoring visits over a 12-week period. Participants randomized to the financial incentives arm (n=90) will receive escalating debit card payments (range \$25-\$70) at each monitoring visit for saliva cotinine levels <30 ng/ml. Control arm participants (n=90) will receive a fixed payment (\$10) at each monitoring visit regardless of their saliva cotinine level. We will use an embedded-experiment mixed methods design, where qualitative ('qual') data collection is embedded within a larger quantitative ('QUAN') RCT with the following specific aims:

**Aim 1. (QUAN)** To determine the effect of the financial incentives intervention on cotinine-verified 7-day smoking abstinence at **A**) the end of treatment (12 weeks) and **B**) 12 weeks after treatment (24 weeks).

*Hypotheses:* Incentive arm participants will have significantly greater cotinine-verified 7-day smoking abstinence than control arm participants at **A**) 12 weeks and **B**) 24 weeks.

**Aim 2. (qual)** To assess why, how, and under what circumstances homeless smokers **A**) achieve abstinence in response to financial incentives and **B**) maintain abstinence after incentives are stopped.

Interviews with participants at **A**) 12 weeks (N=30) and **B**) 24 weeks (N=20) will examine cognitive ('why?'), procedural ('how?'), and contextual ('under what circumstances?') dimensions of their response to financial incentives to generate hypotheses about potential mechanisms for on-treatment and post-treatment effects and to inform modifications of the intervention for future use.

## III. SUBJECT SELECTION

## A. Inclusion and exclusion criteria

To be eligible to participate, individuals must meet **all** of the following criteria:

- 1) Aged  $\geq 18$  years old, assessed by self-report and verified by date of birth.  
*Rationale:* We wish to focus only on adult smokers since adolescent smokers present unique issues that merit separate consideration.
- 2) Lifetime smoker of  $\geq 100$  cigarettes with current daily smoking of  $\geq 5$  cigarettes/day, verified by a saliva cotinine level  $\geq 30$  ng/mL.  
*Rationale:* In order to document smoking abstinence via saliva cotinine levels, trial participants must smoke a sufficient number of cigarettes per day at baseline to be above the accepted threshold of 30 ng/ml for determining smoke exposure.
- 3) Ready to try to quit smoking within the next 3 months, assessed by self-report.  
*Rationale:* We wish to focus on smokers interested in quitting in the near future in order to better isolate a treatment effect.
- 4) Proficient in English, assessed with items asking about native language and self-reported comfort communicating in English among non-native speakers.  
*Rationale:* We do not have the resources to develop study materials or conduct in-person counseling in languages other than English.
- 5) Currently or formerly homeless, assessed by self-report and defined as having ever stayed in an emergency shelter, transitional shelter, abandoned building, place of business, car or other vehicle, church or mission, hotel or motel, or anywhere outside, or having ever stayed in somebody else's house, apartment/condominium, or room due to not having their own place to stay.  
*Rationale:* BHCHP and most HCH programs nationally continue to serve patients after they have gained housing. Additionally, currently and formerly homeless people smoke at similarly high rates, and our epidemiologic analysis of tobacco-attributable cancer and mortality disparities experienced by BHCHP patients included both currently and formerly homeless individuals.
- 6) Have a primary care provider (PCP) within the BHCHP system.  
*Rationale:* This will help ensure that we can communicate efficiently with participants' PCPs via secure, EHR-based messaging systems regarding the safe use of varenicline for smoking cessation.

Individuals will be excluded if they meet **any** of the following criteria:

- 1) Unable to provide informed consent, assessed with knowledge questions about the material presented during the informed consent process that individuals must correctly answer before providing consent to participate.  
*Rationale:* Participants must have a clear understanding of what is involved in the study prior to enrolling.
- 2) Report a history of an allergic reaction to varenicline.  
*Rationale:* Varenicline is a treatment component in both study arms.
- 3) Currently pregnant, planning to become pregnant, or breastfeeding.  
*Rationale:* There is limited information on the safety of varenicline in pregnant women.  
46,47

- 4) Past-month suicidal ideation with plan or intent, or past 12-month history of suicidal behaviors or attempts, based on the primary care screening version of the Columbia Suicide Severity Rating Scale (C-SSRS).  
*Rationale:* Due to past reports of suicidal ideation in patients taking varenicline and limited research on the safety of prescribing varenicline to individuals with recent suicidal ideation or behaviors, we do not believe it is appropriate for these patients to participate in the study.
- 5) Self-reported psychiatric hospitalization in the past 3 months.  
*Rationale:* Varenicline carries a caution label for neuropsychiatric events. There is also limited research on the use of varenicline in patients with unstable mental illness. Hence, we do not feel that it is appropriate to include patients with a recent psychiatric hospitalization in the study.

We will not exclude individuals who use alcohol or other drugs, as long as they meet all of the above eligibility criteria. This decision was made because our prior survey of homeless smokers in Boston suggested that limiting the trial to individuals who do not use other drugs or alcohol would considerably narrow the pool of potentially eligible participants and would severely limit the generalizability of our findings. Concomitant drug and/or alcohol use is common among homeless smokers, and smoking interventions for this population must contend with that reality in order to be applicable. In our pilot RCT, we found that drug and alcohol use, assessed serially over 8 weeks, did not change among participants assigned to receive financial incentives for smoking abstinence. Furthermore, evidence suggests varenicline is both safe and effective in patients with a history of substance use disorder. Because of the potential importance of this issue, we again plan to assess drug and alcohol use with a validated instrument at the beginning, middle, and end of the trial, and to conduct interaction analyses to determine whether drug and alcohol use severity modify the effect of the intervention.

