Depending on space availability, participant preference, and the safety of having in-person interactions based on the status of the COVID-19 pandemic, study participants may complete surveys, coaching sessions, clinician visits, and qualitative interviews in the following ways: **A) On-site in-person:** Staff may administer the surveys/provide coaching in-person at a private area in the clinic space while adhering to physical distancing guidelines. **B) On-site virtual:** Study staff will set up a tablet in a separate on-site room for participants and administer the survey/provide coaching via Microsoft Teams or Enterprise Zoom. **C) Remote and virtual:** Participants with access to a phone, smartphone, or computer can complete the surveys, coaching sessions, clinician visits, and/or interviews virtually with study staff via phone call, Microsoft Teams, or Enterprise Zoom.

Regardless of how participants complete study visits, the PI, [name], and/or the study clinician will be available to advise study staff and speak with participants as needed. Any questions or concerns raised during the consent or enrollment phase in addition to any issues unrelated to varenicline raised throughout the study will be directed to the PI. Any questions or concerns related to varenicline raised throughout the study will be directed first to the study clinician, with the PI serving as back-up.

**1) Screening visit:** Participants will be screened for study eligibility through measurement of the specific data variables listed in section VI.A. Participants who are proactively contacted for recruitment or who contact study staff directly will be offered the option to complete the eligibility screener questions over the phone. If their responses to the questions suggest that they are eligible to participate, they will be invited to meet with study staff in person at JYP to confirm their eligibility with a saliva test for cotinine. If the cotinine saliva test is consistent with current smoking, participants will be able to proceed with enrollment procedures. Both the eligibility screener saliva test and all enrollment procedures need to occur within 2 weeks after the participant answered the eligibility screener questions. Eligible participants who complete all components of the eligibility screening in-person during open screening hours will be asked to come back at a later time to complete enrollment procedures (also within 2 weeks).

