**2) Enrollment visit:** The enrollment visit will occur within 2 weeks after completing the screening visit. If more than 2 weeks has elapsed since screening, participants will need to be rescreened before proceeding to enrollment. During the enrollment visit, eligible participants will provide written informed consent. Enrolled participants will then complete a baseline assessment that includes measurement of the specific data variables listed in section VI.A and a demographics/contact form that includes data variables listed in section VI.A. Participants will also be provided with their CT Payer cards (listed below in section XI.A) during this visit upon completion of the baseline assessment survey. Participants will receive \$25 for completing the

baseline survey. Prior to randomization visits, CRCs will look up enrolled participants in the BHCHP electronic health record (EHR) and will complete a chart review form (data variables to collect listed in section VI.A). Enrolled participants will then be randomized to a study arm in the manner described above.

**3) Randomization and baseline clinician visit:** The randomization and baseline clinician visit will occur within 4 weeks after completing the enrollment visit. If more than 4 weeks has passed since enrollment, participants will first need to undergo repeat screening to confirm their continued eligibility, followed by reassessment of baseline survey measures to inform randomization and identify conditions relevant to varenicline use (see below), before being allowed to proceed to randomization. During the randomization visit, study staff will reveal the participant's group assignment and set up the introductory video which will explain the study components and the study schedule. After the introductory video, staff will provide participants with a study cell phone if applicable (see section V.C.). The participant will then be seen by the study clinician, as described in more detail below. During this visit, participants will be encouraged to set a quit date for the following week. Participants will receive \$10 for attending this visit.

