## **B. Drugs**

Participants in both study arms will be offered a prescription for varenicline, an FDA-approved, first-line smoking cessation medication that has been shown to be safe and effective in at-risk populations, including those with comorbid psychiatric conditions, alcohol use disorder and substance use disorders. In general, varenicline prescriptions will be issued by the study clinician who will meet with participants at the randomization visit to assess their health history and relevant comorbid conditions. In most cases, participants will receive a 1-month prescription for varenicline from the study clinician according to the recommended 7-day loading procedure of 0.5 mg daily on days 1-3 then 0.5 mg twice daily on days 4-7 before reaching the target dose of 1 mg twice daily on day 8.

After the completion of the enrollment visit, study staff will contact the participant's PCP to inform them of their patient's enrollment in a stop smoking study in which varenicline will be offered. Unless the participant reports a history of specific comorbidities, PCP permission will not be required before the study clinician meets with the participant and prescribes varenicline at the typical dosage. However, PCPs will be invited to respond to study staff messages to express any questions or concerns, and if the PCP recommends that varenicline is not prescribed, the study clinician will follow this recommendation. For participants with selected comorbidities, including seizure history, chronic kidney disease, or higher-risk mental states, we will follow a systematic algorithm to ensure safe varenicline prescribing (Appendix 2). Comorbidities will be assessed in various ways, including a) participants' responses to the eligibility screener and baseline survey items related to chronic medical conditions and mental health symptoms, b) review of documented comorbidities within participants' EHR, and c) baseline clinical assessment by the study clinician. The action plans in response to specific comorbidities (as visualized in Appendix 2) are explained further below:

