## VI. BIOSTATISTICAL ANALYSIS

### A. Specific data variables

The specific data elements collected at each visit are as follows:

**1) Screening visit data elements:** This visit will focus on assessing variables related to the inclusion and exclusion criteria. Variables collected during this visit will include:

- First and last name
- Date of birth
- Native language and self-reported comfort communicating in English among non-native speakers
- Ever smoked  $\geq 100$  cigarettes
- Current cigarettes per day
- Saliva cotinine level  $\geq 30$  ng/mL, based on point-of-care testing
- Prior serious allergic reactions to varenicline

- Currently pregnant, planning to become pregnant, or breastfeeding
- Readiness to try quitting smoking within the next 3 months
- Prior experience with homelessness
- Presence of BHCHP electronic health record
- Name of BHCHP PCP (and if PCP has been seen within the past year)
- History of psychiatric hospitalization within the past 3 months
- Suicidal ideation and behavior, based on the C-SSRS
- Among individuals who are eligible and wish to schedule an enrollment visit or who are ineligible but would be interested in attempting screening again in the future, we will collect their current phone number (if any) to facilitate communication about the enrollment visit

**2) Enrollment visit data elements:** When individuals present for enrollment, we will confirm that they have previously screened eligible for the study. For those who wish to enroll in the study, we will collect additional demographic and contact information:

- Gender
- Pronouns
- Social security number
- Current residence or place where sleeping at night
- Current phone number (if any); confirm/update number if previously collected at screening visit
- Emergency contact information
- BHCHP medical record number
- Insurance coverage listed within BHCHP electronic health record

We will also conduct a baseline survey assessing the following variables at the time of enrollment: *Italicized* measures will be collected during follow-up surveys at weeks 12 and 24:

Domains	Measures
Sociodemographic	Race/ethnicity; education; health insurance (all based on items from the 2003 HCH User Survey  and our prior survey work  )
Homelessness	Homelessness episodes and duration; living situation; past-month subsistence difficulties

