#### C. Safety Monitoring

The eligibility criteria for the study are designed to identify individuals who would most likely benefit from the proposed intervention. These criteria represent an expansion of the criteria used in our pilot RCT, enabling the proposed intervention to reach a broader target population. Although all current smokers should be advised to stop smoking and offered assistance in quitting, we believe that the proposed financial incentives approach is best targeted to individuals who are least contemplative about quitting (i.e. planning to quit in the next 3 months). Whether financial incentives might motivate interest in smoking cessation among pre-contemplative smokers is a separate scientific question that merits separate investigation.

During eligibility screening, participants will be asked about potential contraindications to varenicline, including questions about suicidality via the primary care screening version of the C-SSRS (see Appendix 3). Individuals at low risk of suicide will be allowed to participate while being made aware of available behavioral health care resources, including 24-hour crisis line numbers and on-site mental health services at BHCHP. Individuals at moderate risk of suicide only due to history of suicidal behavior >12 months prior (and not due to current suicidal thoughts) will be allowed to participate if all other criteria are met, and will be made aware of available behavioral health care resources. Individuals at moderate risk of suicide due to history of suicidal behavior in the past 3-12 months (and not due to current suicidal thoughts) will be excluded and made aware of available behavioral health care resources. Individuals at moderate risk of suicide due to suicidal thoughts with methods but without intent will be excluded from the study, provided 24-hour crisis line numbers, and encouraged to make an appointment with a behavioral health clinician (at BHCHP or elsewhere) within 3 business days.

Individuals at high risk of suicide due to past 3-month suicidal behavior (with no current suicidal intent) will also be excluded from the study and encouraged to make an appointment with a behavioral health clinician within 3 business days. Individuals at high risk of suicide due to current suicidal intent based on the C-SSRS will be excluded from the study and referred immediately for an urgent on-site same-day mental health evaluation by BHCHP clinical staff.

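### Exclusion 2 bars any allergic reaction to varenicline, but the screening variable that applies it records only serious ones; exclusion 4 also needs one word to match the IX.C triage

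*Combined protocol and SAP*

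**What the plan says.** **Allergy.** Exclusion 2 in section III.A applies to people who "Report a history of an allergic reaction to varenicline". It has no severity qualifier, and its rationale is that varenicline is a treatment component of both arms. Section V.A.1 describes how the criteria are applied: "Participants will be screened for study eligibility through measurement of the specific data variables listed in section VI.A". Among the screening variables in VI.A.1, the allergy entry is "Prior serious allergic reactions to varenicline".

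**Suicidality.** Exclusion 4 in section III.A reads "Past-month suicidal ideation with plan or intent, or past 12-month history of suicidal behaviors or attempts", and bases the assessment on the primary care screening version of the C-SSRS. Section IX.C gives the triage for that instrument. It opens with "During eligibility screening, participants will be asked about potential contraindications to varenicline, including questions about suicidality" and includes this rule: "Individuals at moderate risk of suicide due to suicidal thoughts with methods but without intent will be excluded from the study".

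**Later checks.** Section V.A.2 has coordinators look up enrolled participants in the health record before the randomization visit, where they "will complete a chart review form (data variables to collect listed in section VI.A"). Section V.B has the PCP told of the enrollment and lets the PCP veto varenicline. Section V.A.4 has the study clinician review survey answers, the health record and self-reported history before prescribing.

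**The concern.** An entry rule should read the same where it is stated and where it is applied. For allergy, the applied wording is the looser of the two, which is the unsafe direction. Exclusion 2 turns on what the person reports, so the wording of the question largely decides the answer. Someone asked only about serious reactions can truthfully say no and pass, although the criterion excludes them. What is at stake is whether a person with a known reaction to the drug enters a trial that will offer it.

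For suicidality the difference runs the other way. The triage is stricter than the criterion as worded, so the issue is that the criteria list and the triage should state one rule.

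**Working it through.** The plan states no figure on this point and no arithmetic applies. The check is a comparison of texts, all from the current protocol.

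**Step 1: allergy, rule against variable.**

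| Place | Scope |
|---|---|
| III.A, exclusion 2 | Any reported allergic reaction to varenicline |
| V.A.1 | Eligibility is determined by measuring the VI.A variables |
| VI.A.1 | Serious allergic reactions only |

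The group on which the two scopes disagree is people with a prior non-serious reaction. They are excluded under III.A and are not captured by the VI.A.1 variable as worded. No other text reconciles the two.

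**Step 2: is the gap closed later?** I looked for a later step that names varenicline allergy.

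- The baseline survey table in VI.A.2 covers chronic medical conditions and mental health but lists no allergy item.
- V.A.2 says the chart review variables are in VI.A, but VI.A as supplied contains no chart review list. Nothing can be concluded about whether that form covers allergy.
- V.B, V.A.2 and V.A.4 provide general checks: record review before the randomization visit, a PCP veto, and the clinician's own history. V.B also lets the clinician hold the prescription if something missed at screening comes to light.

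These are real backstops, but none is specific to allergy in the text supplied. Under V.A.3 the assignment is revealed before the clinician sees the participant. The clinician's check can therefore withhold the drug but cannot prevent randomization of someone who should have been screened out. The chart review and PCP contact come after enrollment. The chart review precedes the randomization visit, so it could prompt a correction in time.

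**Step 3: where else the screener is used.** V.A.3 requires repeat screening if more than 4 weeks pass after enrollment. V.H applies the same screener questions to the 11 participants enrolled before the pause, some of whom may already have been randomized. The documents do not say whether any of them had taken varenicline.

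**Step 4: suicidality, rule against triage.**

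| Group | Exclusion 4 (III.A) | IX.C triage |
|---|---|---|
| Suicidal behavior within 12 months | Excluded | Excluded (past 3 months, and 3-12 months) |
| Ideation with intent | Excluded | Excluded |
| Thoughts with methods, without intent | Not named, unless 'plan' covers it | Excluded |
| Behavior more than 12 months ago only | Not excluded | Allowed |

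V.B fits IX.C: the only moderate-risk group it lets proceed, subject to PCP permission, is behavior over 12 months ago. The two applied sections agree, and only the wording of exclusion 4 falls short.

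**Step 5: statistical consequences.** The screening item is put to everyone in the same form. Except for any restarted participant under V.H who already had an assignment, this happens before randomization. Nothing here changes the sample size of 90 per arm, the power statement in VI.D, or the intention-to-treat analysis of the primary outcome in VI.C.

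**The case against.** The best reply on allergy is that VI.A.1 is a list of short data labels, not a set of rules. Other entries, such as those for cigarettes per day and prior homelessness, also name a topic and leave the threshold to III.A. The form staff read from was not supplied and may ask about any reaction. This has force, and it is why the point is conditional. But the label does more than name a topic: it adds a severity qualifier that the criterion lacks, and V.A.1 makes the list the route by which eligibility is judged.

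A reader might go further and infer that people with a known reaction will be given varenicline. The documents do not support that. The record review, PCP veto and clinician history may each catch the case, and participants may decline the drug. Nor does the absence of an allergy action plan in V.B show neglect. That section, introduced with "For participants with selected comorbidities, including seizure history, chronic kidney disease, or higher-risk mental states", manages comorbidities in people already found eligible, and an exclusion would not be expected there.

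On suicidality, a reader might infer that people with thoughts and methods can enter the trial. The documents do not support that either. Exclusion 4 defers to the C-SSRS, IX.C sets the decision for that instrument at eligibility screening, and no section admits this group. 'Plan' in exclusion 4 may have been meant to cover 'methods'; the scale in Appendix 3 was not supplied, so this cannot be settled. The objection stands to the extent that this part is alignment of wording and not a gap in practice.

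**Conclusion.** The allergy mismatch holds: screening carried out as V.A.1 and VI.A.1 are written could pass a person whom exclusion 2 bars. It is minor. Its reach is limited to people with a prior non-serious reaction to varenicline, and general checks after enrollment may still identify them. The documents give no number for this group and I offer none. The conclusion assumes that the screening question follows the VI.A.1 label; if the form already asks about any reaction, only the protocol text needs correcting.

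The suicidality difference is a secondary matter of wording, since the stricter rule is the one set out for use at screening. Neither part affects power or the primary analysis.

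**What to change.** 1. In VI.A.1, delete 'serious' from the allergy element so that it matches exclusion 2. Make the same deletion in the screening form if it uses that word.
2. In exclusion 4, add 'methods' to the ideation clause (for example: past-month ideation with methods, plan or intent) so that it matches IX.C, once the study clinicians confirm that IX.C is the intended rule.

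The cost is two short text edits and at most one form item. Neither edit changes the design, the sample size or the analysis.
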